[figure not shown]

## BACKGROUND

There is a strong experimental basis to support the study of oxytocin by the spinal route for analgesia in humans. Oxytocin containing cells in the dorsal parvocellular division of the paraventricular nucleus (PVN) project to the spinal cord (1). Noxious stimulation activates these cells via the A1 noradrenergic relay in the pons (2) and produces analgesia by spinal release of oxytocin, since intrathecal injection of an oxytocin receptor antagonist worsens pain behaviors from peripheral inflammation (3). Direct electrical stimulation of the PVN reduces dorsal horn neuronal responses to noxious stimulation, and this is blocked by administration of sequestering antibody for oxytocin (4). Similarly, direct electrical stimulation of the PVN reduces behavioral sensitivity in a model of chronic neuropathic pain, and this effect is blocked by an oxytocin receptor antagonist (5). Intrathecal injection of oxytocin in normal rats reduces dorsal horn neuronal responses to noxious stimuli (6) as well as behavioral responses to noxious thermal (3), mechanical (3), and chemical (7) stimuli. Finally, intrathecal injection of oxytocin in rat models of chronic pain also reduces dorsal horn neuronal responses to sensory stimulation (6) as well as behavioral responses to thermal (5) and mechanical (7) stimuli.

Many compounds and manipulations produce evidence of analgesia in rodents, but most studies, including the ones cited for oxytocin above, rely on reflex withdrawal responses to stimulation or electrophysiologic responses in individual cells. As such, the relevance of these observations to spontaneous pain in humans is far from certain. Two observations, however, strongly suggest that intrathecal oxytocin would be analgesic in humans.

[figure not shown]
The first, most direct evidence, is a report from China of 608 patients with chronic low back pain and 369 patients with acute low back pain who received single intrathecal injections of oxytocin (8). Intrathecal oxytocin produced acute analgesia in both settings, with nearly

[figure not shown]
**Figure 1.** Percentage of patients with complete pain relief from intrathecal injection of oxytocin.

universal complete pain relief reported at doses of approximately 30  $\mu\text{g}$  per injection for chronic low back pain and 60  $\mu\text{g}$  per injection for acute low back pain (Figure 1). Duration of analgesia was dose dependent, with < 1 hr analgesia from approximately 7  $\mu\text{g}$  per injection and > 5 hr analgesia from approximately 60  $\mu\text{g}$  per injection.

The second line of evidence comes from our clinical observations in obstetric patients. Physical injury, whether from trauma or surgery, is recognized as an important cause of chronic pain, and the incidence of chronic pain after surgery ranges from 10 to 40%, depending on the procedure (9). We recently completed a clinical trial of over 1200 women examining the incidence of chronic pain after vaginal and cesarean delivery. Although approximately 10% of women had pain 2 months after delivery (10), the incidence of pain one year after delivery was remarkably low (95% confidence limit for pain at one year of 0.7%). This is at least an order of magnitude lower than that reported from any other abdominal surgery, including superficial surgery like inguinal herniorrhaphy (9). We hypothesized, based on these studies, that a factor which is present during pregnancy may be protective of chronic pain. We therefore examined hypersensitivity in rats following a surgery (spinal nerve ligation) which is commonly used as a model of neuropathic pain. To our surprise, this surgery produced similar degrees of hypersensitivity when performed during pregnancy than in nonpregnant animals (Figure 2). In contrast to this lack of effect of pregnancy, the degree of hypersensitivity significantly diminished for several weeks after delivery, abruptly returning when the pups were weaned from

**Figure 2.** Withdrawal threshold drops similarly after spinal nerve ligation (SNL, a model of neuropathic pain) in pregnant and nonpregnant animals, but this hypersensitivity is alleviated after delivery. Colored areas are 95% CIs.

**Figure 3.** In animals with SNL performed during pregnancy, withdrawal threshold drops abruptly when pups are weaned at 17 days, but when SNL is done on the day of delivery, withdrawal threshold never changes from control.

the dams (Figure 3). When nerve injury surgery was performed on the same day as delivery, hypersensitivity never developed, mimicking the clinical trial results of a lack of chronic pain from surgical or vaginal delivery (Figure 3).

We subsequently performed several studies which suggest that spinal release of oxytocin represents the protective factor against chronic pain after childbirth. Intrathecal injection of the specific oxytocin receptor antagonist, atosiban, temporarily reverses the blockade of nerve injury induced hypersensitivity in the postpartum period in rats. Similarly, intracerebroventricular administration of the  $\alpha$ -adrenoceptor antagonist, phentolamine, which is known to block the effects of lactation on activation of oxytocin-containing neurons in the paraventricular nucleus (PVN) of the hypothalamus, also temporarily reverses the blockade of nerve injury induced hypersensitivity in the postpartum period in rats. Finally, protection against hypersensitivity from nerve injury is abruptly reversed when pups are separated from dams for 24 hr, and this is accompanied by a large decrease in oxytocin concentration in cerebrospinal fluid. Although we are currently performing more clinical and laboratory studies to further define this mechanism, these data suggest that spinal oxytocin receptor stimulation in the period immediately following delivery protects against the generation of injury-induced hypersensitivity and subsequent chronic pain.

We recently completed a Phase 1 safety study of intrathecal oxytocin and observed no serious adverse events over the dose range studied (5-150  $\mu$ g). One subject at the 150  $\mu$ g dose had transient subjective numbness in sacral dermatomes, but this was preceded by a vasovagal episode beginning just prior to spinal injection, and this did not occur in other subjects at this dose. There were no objective signs of motor or sensory dysfunction in any volunteer, and blood pressure, heart rate, sensorium, corrected QT interval and serum sodium were unaffected.

We anticipate that oxytocin will be effective after spinal injection in humans to acutely relieve chronic neuropathic pain. For these future studies, we will use a cross over, controlled and blinded study of intrathecal oxytocin in patients with neuropathic pain below the umbilicus, with primary outcome being visual analog score for pain and secondary outcomes being areas of increased pain sensation to a normally painful stimulus (hyperalgesia) and pain sensation to what previously was an innocuous stimulus (allodynia).

## Protocol

### **Efficacy of Intrathecal Oxytocin in Patients with Neuropathic Pain**

**GOAL:** Determine the effect of intrathecal oxytocin on pain and areas and intensity of hyperalgesia and allodynia in patients with chronic neuropathic pain.

**METHODS:** Equal numbers of healthy men and women will be recruited. On a day at least 3 days before study, patients will come to the CTSI Clinical Research Unit (CRU) to review the informed consent, confirm eligibility criteria, and be trained to rate pain in response to heat applied to an area of normal skin without ongoing pain using a Peltier controlled thermode, and to rate pain in response to 225 mN von Frey filament testing within the area of hyperalgesia, if present.

Subjects will come to the CTSI CRU at least 3 days later and be randomized into one of 2 groups of 20 subjects each to receive, in a double-blind manner, intrathecal saline or intrathecal oxytocin, 100 µg. The solutions will be prepared and dispensed to this institution under IND approval and regulation from the Food and Drug Administration and will be released to the investigators through the research pharmacy at Wake Forest School of Medicine. Following subject rating of their ongoing pain and mapping of areas of allodynia and hyperalgesia, as well as rating of pain by a 225 mN von Frey filament applied in the area of hyperalgesia, an intrathecal injection of the study solution in a 3 ml volume will be performed via a #27 or #25 Whitacre needle inserted in a lower lumbar interspace. Subjects will rate their ongoing pain and that from the von Frey filament in the area of hyperalgesia, and we will map the areas of hyperalgesia and allodynia at 30, 60, 90, 120, 180, and 240 min after injection. Subjects will return a second time to the CTSI CRU at least 1 week after the first study session and the same procedures will be performed, except that they will receive the other intrathecal study drug solution (e.g., if they received saline on study session 1, they will receive oxytocin on study session 2).

We will abandon an individual participant's study and schedule another participant to receive the same randomization, should we be unable to successfully place the spinal needle to inject study solution. In our experience, this occurs in less than 10% of participants. Subjects will be recruited at Wake Forest School of Medicine pain clinics, and Orthopaedic and Podiatry

clinics at the Wake Forest Davie County facility. Subjects will also be recruited from our existing database BG 05-468 and we will also utilize the Clinical Translational Science Institute's (CTSI) Enterprise Data Warehouse (EDW) and approved advertising in the community for potential subjects.

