## **STUDY DESIGN**

Inclusion Criteria: We request permission to study up to 44 subjects so that we will have 40 evaluable subjects.

1. Male or female  $\geq 18$  and  $< 70$  years of age, with a BMI  $< 40$ .
2. Presence of neuropathic pain for  $> 6$  months, with primary pain area below the umbilicus.

We will focus recruitment efforts on low back pain with a neuropathic component to the lower extremities, but will accept other causes of neuropathic pain.

3. Female subjects of child-bearing potential and those  $< 1$  year post-menopausal, must be practicing highly effective methods of birth control such as hormonal methods (e.g., combined oral, implantable, injectable, or transdermal contraceptives), double barrier methods (e.g., condoms, sponge, diaphragm, or vaginal ring plus spermicidal jellies or cream), or total abstinence from heterosexual intercourse for a minimum of 1 full cycle before study drug administration.

4. Blood pressure (systolic 90-150 mmHg; diastolic 50-90 mmHg) resting heart rate 45-100 beats per minute.

5. All subjects must be vaccinated against SARS-CoV-2, with proof via vaccination card or the NC HHS form.

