#### Completion of Day 2 Assessment

1. Vital signs are within 20% of those on admission to the CRU
2. He or she can ambulate without difficulty (no motor, balance affects).
3. Someone other than the subject will take the subject home (requirement for participation).
4. Subject promises to stay home where he or she can be contacted by telephone (requirement for participation).

We will instruct the subject to call us, providing beeper and telephone numbers of the research nurse and the investigators should he have any questions or problems. The research nurse will call the subject at 6 hours and 12 hours post-spinal study drug injection inquiring about any perceived problems.

Study Visit 3: Approximately 24 hours after the spinal oxytocin injection the subject will report to the CTSI CRU to have a blood sample drawn for a Basic Metabolic Panel to assess serum sodium levels.

Study Visit 4: At least one week after Study Visit 2 the subject will return to the CTSI CRU for intrathecal injection of the cross over study solution. All procedures will be the same as Study Visit 2.

Study Visit 5: Approximately 24 hours after the spinal oxytocin injection the subject will report to the CTSI CRU to have a blood sample drawn for a Basic Metabolic Panel to assess serum sodium levels.

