### **Subject Payment**

Participants will be paid a total of \$800 according to the following payment schedule which we have used throughout the last 2 cycles of this grant's protocols. We believe that this payment schedule is fair and appropriate, paying for each procedure attempted and an additional payment for completion of the entire study.

Placement of IV on each study day: \$25

If IV placement unsuccessful, the volunteer is paid and the study abandoned.

Placement of Spinal on each study day: \$100 and study drug administration

If the 1st spinal is attempted but proves unsuccessful, the volunteer is paid \$100 and the study abandoned.

- Completion of study Visit 2 (first spinal injection): \$150

- Completion of study Visit 4: (second spinal injection): \$250
- Completion of entire study (completion of all study related procedures):  
\$150

Volunteer must complete all of the above phases to receive the total payment.

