### **STATISTICAL RATIONALE**

**Primary outcome measure** will be ongoing pain by visual analog scale.

**Group comparison:** Pain will be compared using a repeated measures ANCOVA.

**Power analysis:** Based on previously published work by us with this model in which the patient population has an ongoing pain level of  $4.3 \pm 2.0$  and a reduction in pain 60 min after injection of  $0.9 \pm 1.5$ , a group size of 40 will allow us to observe a difference between placebo and treatment of 0.7 with  $\alpha=0.05$  and  $1-\beta=0.80$ .

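### Does the plan need an added rule for a participant whose second crossover session cannot take place?

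*Combined protocol and SAP*

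**What the plan says.** The trial is a two-session crossover, saline in one session and oxytocin in the other, with 20 subjects per order. Five places bear on a session that cannot be carried out.

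- **Protocol, METHODS.** After describing both sessions, the text says the participant's study is abandoned and the team will "schedule another participant to receive the same randomization, should we be unable to successfully place the spinal needle". It adds: "In our experience, this occurs in less than 10% of participants".
- **Subject Payment.** For the spinal: "If the 1st spinal is attempted but proves unsuccessful, the volunteer is paid" and the study is abandoned. For the IV, under the item "Placement of IV on each study day": "If IV placement unsuccessful, the volunteer is paid and the study abandoned".
- **Study Visit 4** (under Completion of Day 2 Assessment). "All procedures will be the same as Study Visit 2". Needle or IV failure can therefore occur after session 1 data exist.
- **STUDY DESIGN, Inclusion Criteria.** "We request permission to study up to 44 subjects so that we will have 40 evaluable subjects". Evaluable is not defined.
- **STATISTICAL RATIONALE.** "Pain will be compared using a repeated measures ANCOVA". No analysis set is named, and nothing is said about a missing session.

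**The concern.** Set side by side, METHODS and Subject Payment do not match exactly. One gives a needle-failure rule with no session attached; the other speaks of the first spinal only. Replacement is stated for needle failure and not for IV failure. With evaluable undefined and no analysis set, it is not written down whether a participant with session 1 only counts among the 40, or whether that person's pain scores enter the ANCOVA.

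In a crossover this is a reasonable thing to ask. If the decision is made case by case after session 1 scores have been seen, the analysed group could be shaped by the data. If the 44 places yield exactly 40 evaluable subjects, up to 4 (4/44 = 9.1%) could have had one injection and no stated place in the efficacy analysis. That upper figure requires every loss to fall after session 1.

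**Working it through.** **1. What is actually open.** A failed IV is covered on either study day: the study is abandoned. The needle rule in METHODS follows the description of both sessions and is limited to neither, so read literally it includes the second spinal. The payment line is narrower and concerns what is paid. Three things remain unstated: replacement after IV failure, the meaning of evaluable, and the use of session 1 pain data when session 2 is missing.

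**2. What evaluable must mean for the sample size to work.** Inputs from STATISTICAL RATIONALE: difference 0.7, α = 0.05, power 0.80, n = 40, SD of the pain reduction 1.5. Assumptions: the SD of the within-patient oxytocin-minus-placebo difference is also 1.5 (equivalent to a between-session correlation of 0.5, since 1.5 × √(2 × (1 − 0.5)) = 1.5), and the test is two-sided.

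The paired t-test has noncentrality 0.7/1.5 × √n on n − 1 degrees of freedom:

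| Complete pairs | Noncentrality | Power |
|---|---|---|
| 36 | 2.80 | 77.7% |
| 38 | 2.88 | 80.0% (just below) |
| 39 | 2.91 | 81.1% |
| 40 | 2.95 | 82.1% |

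The smallest n reaching 0.80 is 39, against 40 stated, so the plan's figure reproduces. With parallel groups and the same SD, 73 per group would be needed. The 40 are therefore 40 people with both sessions.

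**3. Does 44 cover the stated failure rate?** The break-even loss is 1 − 40/44 = 9.1%. Taking the rate per participant, as METHODS words it, with X ~ Binomial(44, 1 − f):

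| Loss f | Expected completers | P(X ≥ 40) |
|---|---|---|
| 5% | 41.8 | 93% |
| 8% | 40.5 | 73% |
| 10% (the text says less than this) | 39.6 | 55% |

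As a harsher assumption, let 10% fail independently at each session. Then 44 × 0.9 × 0.9 = 35.6 complete both and 44 × 0.9 × 0.1 = 4.0 have session 1 only. That is about 36 pairs, and the power loss is 82.1 − 77.7 = 4.4 percentage points.

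**4. What would the one-session data add?** Take 36 pairs, 18 per order, plus 4 session 1-only participants, 2 per order, in a model with a period effect. In units of 1/variance of a single score, the pairs carry information 36/(2(1 − ρ)) on the treatment difference. The four singles carry 4/4 = 1. The relative gain is 2(1 − ρ)/36:

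- ρ = 0.3: 1.4/36 = 3.9%
- ρ = 0.5: 1.0/36 = 2.8%
- ρ = 0.7: 0.6/36 = 1.7%

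The correlations are assumed; the documents give none. Including or omitting these participants hardly alters the precision of the estimate.

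**5. Can selection favour one treatment?** METHODS make the injections double-blind. Failure to place a needle or an IV is procedural, and nothing in the documents links it to what was given at least a week before. Replacement by a participant with the same randomization also keeps the two orders balanced.

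**6. Safety.** Side-effect reporting (Safety and Monitoring), adverse-event reporting to the monitoring committee, IRB and FDA (Data Safety Monitoring Plan) and the calls up to 6 months (Long-term Follow-up) are not restricted to those who finish both sessions.

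**The case for a change.** The best case for a change is that it costs a few lines. The statistical section names no analysis set. Under the Data Safety Monitoring Plan the investigator reviews data after each subject's treatment, so session 1 scores may have been seen before anyone decides who counts. The margin of four is thin: with an assumed further 2% lost to IV failure or non-return, the chance of 40 completers is 82% at 5% needle failure and 56% at 8%. Nor does the text say outright whether its failure rate spans both spinals.

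Much of this is accurate. The definition of evaluable is missing, replacement after IV failure is unstated, and the payment wording is narrower than METHODS. Someone who chooses not to return, unlike someone whose needle cannot be placed, might do so because of session 1, so blinding and the procedural nature of failure do not answer that case completely.

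What does not stand is the consequence. The scores under review are blinded. Missing the target by four pairs costs under five points of power. Non-return is ordinary crossover drop-out: a repeated-measures model can retain the session 1 scores, the complete-pairs result can be shown beside it, and with so few people the two should be close. The 44, the 40 and the primary ANCOVA would all stay the same after any clarification.

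**Conclusion.** No change to the plan follows. The gap is one of wording, and a competent analyst would fill it in the way the paired sample size already implies: evaluable means both injections received with pain rated after each, and session 1-only data are reported as such. Following the plan as written would still give a sound result.

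The size is at most about 4.4 percentage points of power (40 to 36 pairs), and that under a harsher failure rate than the per-participant wording suggests. One-session participants bear on 1.7% to 3.9% of the information. These figures rest on a within-patient SD of 1.5, two-sided testing and correlations of 0.3 to 0.7, none of which the documents state. With a different SD the power figures would move, but the few one-session participants would remain a minor part of the evidence. The difference between METHODS and Subject Payment over a failed second spinal is a loose end in the drafting, best tidied whenever the text is next revised; it gives no reason to doubt the efficacy comparison or the safety reporting.

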## **STUDY DESIGN**

Inclusion Criteria: We request permission to study up to 44 subjects so that we will have 40 evaluable subjects.

1. Male or female  $\geq 18$  and  $< 70$  years of age, with a BMI  $< 40$ .
2. Presence of neuropathic pain for  $> 6$  months, with primary pain area below the umbilicus.

We will focus recruitment efforts on low back pain with a neuropathic component to the lower extremities, but will accept other causes of neuropathic pain.

3. Female subjects of child-bearing potential and those  $< 1$  year post-menopausal, must be practicing highly effective methods of birth control such as hormonal methods (e.g., combined oral, implantable, injectable, or transdermal contraceptives), double barrier methods (e.g., condoms, sponge, diaphragm, or vaginal ring plus spermicidal jellies or cream), or total abstinence from heterosexual intercourse for a minimum of 1 full cycle before study drug administration.

4. Blood pressure (systolic 90-150 mmHg; diastolic 50-90 mmHg) resting heart rate 45-100 beats per minute.

5. All subjects must be vaccinated against SARS-CoV-2, with proof via vaccination card or the NC HHS form.

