### **RANDOMIZATION GROUPS**

A computer generated randomization will be used to determine the group for each subject. Subjects will be randomized to receive an intrathecal injection of the saline placebo or 100 µg oxytocin on the first study visit, with the other on the second.

**Study Visit 1:** The participant will report to the CTSI Clinical Research Unit (CRU) at least 3 days prior to study visit 2. The participant will review and sign the Informed Consent. After informed consent is adequately obtained, a detailed medical history will be obtained from the participant, female participants will have blood drawn and sent to the laboratory to determine pregnancy status. Participants will be trained to estimate pain quantitatively using a 2 cm^2 peltier controlled thermode (TSA®) applied to an area of normal skin outside the area of ongoing pain. Typically, the participant is exposed to temperatures between 38 and 51 C using a random staircase method.

During this training period, the participant's blood pressure, heart rate, and peripheral oxyhemoglobin saturation will be recorded. A 12 Lead electrocardiogram (ECG) will also be performed.

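### Does the lack of a minimum pain score at entry undermine a trial whose primary outcome is ongoing pain?

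*Combined protocol and SAP*

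**What the plan says.** The inclusion list under STUDY DESIGN requires neuropathic pain present for more than 6 months, "with primary pain area below the umbilicus". Neither that list nor the Exclusion Criteria names a pain score. The enrolment limit reads: "We request permission to study up to 44 subjects so that we will have 40 evaluable subjects".

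At Study Visit 1 (under RANDOMIZATION GROUPS), "The participant will review and sign the Informed Consent", and training follows: "Participants will be trained to estimate pain quantitatively using a 2 cm"-square thermode on normal skin. No rating of ongoing pain is listed at that visit. On the injection day ongoing pain is rated beforehand (Protocol, METHODS: "Following subject rating of their ongoing pain and mapping of areas of allodynia and hyperalgesia"), but proceeding does not depend on the score.

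The GOAL is wider than ongoing pain: "Determine the effect of intrathecal oxytocin on pain and areas and intensity of hyperalgesia and allodynia in patients with chronic neuropathic pain". STATISTICAL RATIONALE names the primary outcome, which "will be ongoing pain by visual analog scale", and plans from earlier work by the same group in which "the patient population has an ongoing pain level of" 4.3 ± 2.0, with a fall of 0.9 ± 1.5 at 60 minutes.

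**The concern.** A pain score cannot fall below zero. A patient who starts at 0 or 1 cannot show a difference of 0.7 on top of any fall after saline, so the observed effect shrinks and power with it. Each patient is also due two dural punctures, whose risks the RISKS section lists. If many enrolled patients had little pain to relieve, the trial would expose people who can contribute little to its main question and might miss a real effect. Nothing in the entry rules secures the planned mean of 4.3, and recruitment includes community advertising.

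**Working it through.** **Inputs.** From STATISTICAL RATIONALE: baseline 4.3 ± 2.0; fall at 60 minutes 0.9 ± 1.5; difference 0.7; group size 40; alpha 0.05; power 0.80. From STUDY DESIGN: 44 enrolled for 40 evaluable. Assumed, because the document does not say: a 0–10 scale, two-sided alpha, ± meaning SD, 1.5 as the SD of the within-patient difference, and a roughly normal baseline.

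**1. The plan's own figure.** Paired t test, noncentrality = 0.7 × √40 / 1.5 = 2.95 on 39 degrees of freedom, critical value 2.02. Power is 82.1%. The difference detectable with 80% power is 0.681, which rounds to the stated 0.7. The sample size is reproduced.

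**2. How many patients start low.**
- Below 2: Φ((2 − 4.3)/2.0) = Φ(−1.15) = 12.5%, or 5 of 40. Other shapes with the same mean and SD give 7–17%.
- Below 1: Φ(−1.65) = 4.9%, or 2 of 40. Other shapes give 0.1–3.5%.

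Patients with almost no pain therefore number 0 to 2 of 40. Those below 2 can still show part of a true 0.7: 0.32, 0.47 or 0.51 if the saline fall is 0.9, 0.2 or 0.

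**3. Effect on the trial.** Simulation: baseline clipped to 0–10 and stable between visits; fall in each session = saline fall (plus 0.7 for oxytocin) + normal error with SD 1.5/√2, capped at the starting score; power from the paired t test with n = 40. This simplifies the planned repeated measures ANCOVA to one time point.

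| Saline fall | Mean difference, no threshold | Power, no threshold | Mean difference, threshold 2 | Power, threshold 2 | Gain (points) |
|---|---|---|---|---|---|
| 0.9 | 0.635 | 79.1% | 0.681 | 81.5% | 2.4 |
| 0.2 | 0.668 | 80.9% | 0.696 | 82.0% | 1.1 |
| 0 | 0.674 | 81.2% | 0.698 | 82.2% | 1.0 |

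Repeat runs agree within about 0.3 points. Over the other baseline shapes and visit-to-visit correlations of 0.6–1.0, the gain is 0.1 to 2.4 points.

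**4. What a threshold of 2 would cost.**
- To randomize 44, about 44/0.875 = 50 must be screened.
- If the limit of 44 covers everyone screened, 44 × 0.875 = 38.5 are enrolled and 38.5 × 40/44 = 35 are evaluable. Power under fixed relief is then about 74–77%, below the plan as it stands.
- Enrolling all 50 without a threshold gives about 50 × 40/44 ≈ 45 evaluable and 84–86% power, against 80–82% for 40 evaluable with a threshold.

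**5. Whether a Visit 1 threshold would work.** Pain varies between visits. With a threshold of 2 at Visit 1 and equal correlation between visits, the share of patients who still start at least one injection session below 2 is 9.6% (correlation 0.8) or 14.1% (0.6). Without a threshold it is 17.6% or 19.7%. At 0.6, under a third of the problem is removed (1 − 14.1/19.7 = 28%).

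**6. Bias.** Each patient receives both solutions, so low scorers enter both sides of the comparison. A floor pulls the estimated difference towards zero; it does not create an apparent effect.

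**The case for a change.** The strongest case is that the gap is plain in the text and cheap to close: one criterion line and one rating at an existing visit. The nearest safeguard, exclusion criterion 2, is a general investigator judgement that names no pain level.

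The small power effect also depends on its assumptions. If relief is proportional to starting pain, a threshold of 2 gains 1.7 to 3.9 points when variability scales too, and 4.8 to 7.7 when the SD stays constant. A strict cap on relief, at baseline less a 0.9 saline fall with the SD held at 1.5, gives gains of up to 5.2 points. If enrolled patients were milder than planned, at 3.0 ± 2.0, power would be about 74% under fixed relief and 53% under proportional relief.

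These figures stand as sensitivity results, but they do not show a fault. Under proportional relief with a total SD of 1.5, power without a threshold is still about 80–82%, so the threshold adds to a target already met. A milder population would contradict the planning data, and recruitment from pain clinics makes near-zero scorers less likely. The earlier work's entry rules are not shown: if it had no minimum, its figures may already carry the floor effect; if it had one, those figures do not show how many patients would start low here.

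The risk argument has some force, but it is a preference. Every patient gets one oxytocin and one saline injection, the Background describes analgesia lasting hours, and RISKS claims no benefit to participants. Previous Experience in the CRU records intrathecal studies in healthy volunteers as well as patients, so pain has not been a condition for a spinal injection in this programme. A low scorer with marked hyperalgesia or allodynia still serves the stated goal. In fairness, the 84–86% for 45 evaluable patients comes from injecting about six more people; it shows only that the threshold is not the more powerful use of the same screening effort.

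**Conclusion.** The concern does not hold. The plan sets no minimum pain score, but carried out as written it delivers about 78–82% power across the fixed-relief cases examined, against a target of 80%. A threshold of 2 would add between about 0 and 2.4 points. It would reduce power if screening stops at 44, would narrow the population for the hyperalgesia and allodynia outcomes, and would still leave roughly 10–14% of patients starting at least one session below 2. Admitting low scorers is a defensible choice between two reasonable designs.

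This rests on fixed relief, a 0–10 scale, a baseline near the planned 4.3 ± 2.0, and 1.5 as the SD of the within-patient difference. The last is supported because it reproduces the stated 0.7. Proportional relief would make a threshold more attractive without making the present plan inadequate at the planned total SD of 1.5. A clearly milder population would be a departure from the planning figures themselves.
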